5.9 Analysis of items of particular interest

5.9.1 Occurrence of the adverse drug reaction of peripheral nerve disorder and infections

(1) Analysis sets to be used

Safety analysis set, safety analysis set (Hodgkin's lymphoma), and safety analysis set (anaplastic large-cell lymphoma)

(2) Data to be analyzed

The incidence of peripheral nerve disorders considered related to Adcetris will be calculated for each CTCAE grade (the worst one) by symptom of peripheral nerve disorder (peripheral sensory neuropathy, peripheral motor neuropathy, or peripheral neuropathy) and PT (see Section 1.2 for the definition of symptoms of peripheral nerve disorders). For symptoms of peripheral nerve disorders, the number and percentage of patients with peripheral nerve disorder will be calculated. For PT, the number and percentage of peripheral nerve disorder will be calculated. PTs will be presented in ascending order of PT code.

The CTCAE grade (the worst one) is higher in the order of Grades 5, 4, 3, 2, 1, and unknown. If the same patient has multiple occurrences of the same symptom of peripheral nerve disorder or the same PT, the symptom of peripheral nerve disorder or PT with the highest CTCAE grade (the worst one) will be counted for the respective category once per patient:

Data item	Category
CTCAE Grade (the worst one) for peripheral nerve disorders	Grade 1, Grade 2, Grade 3, Grade 4, Grade 5, or unknown

(3) Figure/table number

Tables 5.9.1-1 to 5.9.1-3

5.9.2 Occurrence of peripheral nerve disorders considered related to Adcetris by patient demographics and baseline characteristics and treatment given

(1) Analysis sets to be used

Safety analysis set, safety analysis set (Hodgkin’s lymphoma), and safety analysis set (anaplastic large-cell lymphoma)

(2) Data to be analyzed

For each data item of patient demographics and baseline characteristics and treatment given, patients will be stratified into the categories below, and the incidence of peripheral nerve disorders considered related to Adcetris will be calculated by CTCAE Grade (the worst one). The CTCAE grade (the worst one) is higher in the order of Grades 5, 4, 3, 2, 1, and unknown. If the same patient has multiple occurrences of the same peripheral nerve disorder (PT), the peripheral nerve disorder with the highest CTCAE grade will be counted once for the category:

Data item	Category
CTCAE Grade (the worst one) of peripheral nerve disorder	Grade 1, Grade 2, Grade 3, Grade 4, Grade 5, or unknown

Items and categories of patient demographics and baseline characteristics and treatment given

Data item	Category
Sex	Male or female
Age	<18 years, 18 to 64 years, 65 to 74 years, or ≥75 years
Disease duration	<1 year, <1 to 3 years, <3 to 5years, ≥5 years, or unknown
ECOG Performance Status	0, 1, 2, 3, or 4
Concurrent peripheral nerve disorders	None, Grade 1, Grade 2, Grade 3, Grade 4, or unknown
Weight	<40 kg, <40 to 50 kg, <50 to 60 kg, <60 to 70 kg, or ≥70 kg
Prior ABVD or CHOP	Absent or present
Prior radiotherapy	Absent or present
Prior hematopoietic stem cell transplantation	Absent, present (autologous), present (homologous), present (autologous and homologous), or unknown
Initial dose of Adcetris	<1.2 mg/kg, 1.2 mg/kg, >1.2 mg/kg to <1.8 mg/kg, 1.8 mg/kg, or >1.8 mg/kg
Mean dose of Adcetris	<1.2 mg/kg, 1.2 mg/kg, >1.2 mg/kg to <1.8 mg/kg, 1.8 mg/kg, or >1.8 mg/kg
Dose of Adcetris per 3 weeks	<1.2 mg/kg, 1.2 mg/kg, >1.2 mg/kg to <1.8 mg/kg, 1.8 mg/kg, or >1.8 mg/kg
Concurrent diabetes mellitus	Absent or present

(3) Figure/table number

Tables 5.9.2-1 to 5.9.2-3

5.9.3 Treatment with Adcetris at the onset of peripheral nerve disorders considered related to Adcetris

(1) Analysis sets to be used

Patients included in the safety analysis set and safety analysis set (Hodgkin’s lymphoma) or safety analysis set (anaplastic large-cell lymphoma) who experience peripheral nerve disorders considered related to Adcetris

(2) Data to be analyzed

For each CTCAE Grade (the worst one) of peripheral nerve disorders considered related to Adcetris, patients will be stratified into the categories below, and the incidence of peripheral nerve disorders will be calculated. If the same patient has multiple occurrences of the same peripheral nerve disorder (PT), the total number of occurrences will be calculated per category (for example, if the same patient has one episode of peripheral nerve disorder requiring dose reduction and one episode of peripheral nerve disorder leading to treatment discontinuation, these episodes of peripheral nerve disorder will be counted once for each category). The percentage of peripheral nerve disorders for each category will be calculated using the number of peripheral nerve disorders for each CTCAE grade (the worst one) as the denominator.

For each data item, missing data will be handled as “not provided.”

Data item	Category
Action taken to Adcetris	No action taken or action taken in response to the event or not provided
Specific action taken to Adcetris	Dose reduction, treatment interruption (treatment delay), treatment discontinuation, or not provided

(3) Figure/table number

Tables 5.9.3-1 to 5.9.3-3

5.9.4 Outcome of peripheral nerve disorders (\geq CTCAE Grade 3) considered related to Adcetris by action taken with Adcetris

(1) Analysis sets to be used

Patients included in safety evaluation and patients included in safety evaluation (Hodgkin’s lymphoma) or patients included in safety evaluation (anaplastic large-cell lymphoma) who experience peripheral nerve disorder (\geq CTCAE Grade 3) considered related to Adcetris

(2) Data to be analyzed

For peripheral nerve disorders considered related to Adcetris, patients will be stratified into the categories below for each outcome and the incidence of these peripheral nerve disorders will be calculated. If the same patient has multiple occurrences of peripheral nerve disorder, the total number of occurrences will be calculated per category (for example, if the same patient has one episode of peripheral nerve disorder requiring dose reduction and one episode of peripheral nerve disorder leading to treatment discontinuation, these episodes of peripheral nerve disorder will be counted once for each category).

For each data item, missing data will be handled as “not provided.” The percentage of peripheral nerve disorders for each category will be calculated using the total number of peripheral nerve

disorders for each category as the denominator:

Data item	Category
Action taken to Adcetris	No action taken or action taken in response to the event or not provided
Specific action taken to Adcetris	Dose reduction, treatment interruption (treatment delay), treatment discontinuation, or not provided

(3) Figure/table number

Tables 5.9.4-1 to 5.9.4-3

5.9.5 Occurrence of infections considered related to Adcetris by presence or absence of drugs used for the prevention of infection

(1) Analysis sets to be used

Safety analysis set, safety analysis set (Hodgkin's lymphoma), and safety analysis set (anaplastic large-cell lymphoma)

(2) Data to be analyzed

Patients will be stratified into the categories below and the incidence of infections considered related to Adcetris for each CTCAE grade (the worst one) will be calculated by presence or absence of drugs used for the prevention of infection, using Mann-Whitney U test. The CTCAE grade (the worst one) is higher in the order of Grades 5, 4, 3, 2, 1, and unknown. If the same patient has multiple occurrences of the same infection, the occurrence with the highest CTCAE grade will be counted once for the category.

Similar analyses will be performed by use or non-use of antibiotics/synthetic antibacterial agents or trimethoprim-sulfamethoxazole combinations and by use or non-use of trimethoprim-sulfamethoxazole combinations for bacterial infection, by use or non-use of antifungals for fungal infection, and by use or non-use of antivirals for viral infection.

For patients included in safety evaluation who use antivirals for the prevention of viral infection but experience viral infection, a list of the following items will be generated: patient number, viral infection (name of the infection), age, sex, diagnosis, past history of hematopoietic stem cell transplantation (autologous or homologous), and drugs used for the prevention of infection (antivirals). If the same patient has multiple viral infections, all these viral infections will be counted.

Data item	Category
CTCAE Grade (the worst one) of infections	None, Grade 1, Grade 2, Grade 3, Grade 4, Grade 5, or unknown

(3) Figure/table number

Tables 5.9.5-1 to 5.9.5-3 and 5.9.5-4

5.9.6 Occurrence of infections considered related to Adcetris by presence or absence of prior hematopoietic stem cell transplantation

(1) Analysis sets to be used

Patients included in safety evaluation and patients included in safety evaluation (Hodgkin’s lymphoma) or patients included in safety evaluation (anaplastic large-cell lymphoma)

(2) Data to be analyzed

The incidence of infections considered related to Adcetris for each CTCAE grade (the worst one) will be calculated by presence or absence of prior hematopoietic stem cell transplantation (absent, present [autologous], present [homologous], present [autologous and homologous], or unknown) using Kruskal-Wallis test. The grade category of “unknown” will be excluded from the test.

The CTCAE grade (the worst one) is higher in the order of Grades 5, 4, 3, 2, 1, and unknown. If the same patient has multiple infections, the one with the highest CTCAE grade (the worst one) will be counted once for the category (the worst one).

Similar analyses will be performed for bacterial, fungal, and viral infections.

Data item	Category
CTCAE Grade (the worst one) of infection	None, Grade 1, Grade 2, Grade 3, Grade 4, Grade 5, or unknown

(3) Figure/table number

Tables 5.9.6-1 to 5.9.6-3

5.9.7 Occurrence of neutropenia considered related to Adcetris by patient demographics and baseline characteristics

(1) Analysis sets to be used

Safety analysis set, safety analysis set (Hodgkin’s lymphoma), and safety analysis set (anaplastic large-cell lymphoma)

(2) Data to be analyzed

For each data item of patient demographics and baseline characteristics, patients will be stratified into the categories below, and the incidence of neutropenia considered related to Adcetris will be calculated by CTCAE Grade (the worst one). The CTCAE grade (the worst one) is higher in the order of Grades 5, 4, 3, 2, 1, and unknown. If the same patient has multiple occurrences of neutropenia, the event with the highest CTCAE grade will be counted once.

Data item	Category
CTCAE Grade (the worst one) of neutropenia	Grade 1, Grade 2, Grade 3, Grade 4, Grade 5, or unknown

Items and categories of patient demographics and baseline characteristics

Data item	Category
Prior hematopoietic stem cell transplantation	Absent, present (autologous), present (homologous), present (autologous and homologous), or unknown

Degree of decreased neutrophil count at baseline	No decrease, Grade 1, Grade 2, Grade 3, Grade 4, or unknown
Drugs used for the prevention of infection	Absent or present
Specific drug(s) used for the prevention of infection	Antibiotics/synthetic antibacterial agents, antifungals, antivirals, trimethoprim-sulfamethoxazole combinations, or other

(3) Figure/table number

Tables 5.9.7-1 to 5.9.7-3

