### 3.2 Rationale

It is expected that the detailed evaluation of peripheral nerve disorders, infections, neutropenia, infusion reactions, and pulmonary disorders will help better understand the safety profile of Adcetris in the routine clinical setting, which will lead to the assessment of the risk-benefit balance of the drug.

The frequencies of peripheral nerve disorders, infections, neutropenia ( $\geq$ Grade 3), infusion reaction, and pulmonary disorder in non-Japanese phase 2 studies (pooled study data from a study in patients with Hodgkin's lymphoma [SG035-0003, 102 patients] and a study in patients with systemic anaplastic large cell lymphoma [SG035-0004, 58 patients]) were 56%, 61%, 20%, 11%, and 6%, respectively.

Observation of infusion reactions with the lowest frequency of  $\geq 10$  patients, aside from pulmonary disorders, with a probability of 95% would require 140 patients, which was therefore determined to be the estimated enrollment. It is estimated that when the number of patients enrolled reaches 140 patients,  $\geq 4$  patients have adverse events of pulmonary disorder with a probability of 95%.

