### a) Peripheral nerve disorders

Peripheral nerve disorders are frequently observed after treatment with Adcetris. If the event of peripheral nerve disorder becomes severe, it is difficult to continue treatment with Adcetris. It is important to control the onset of the event to allow for continuation of treatment (including dose reduction and restart of treatment after treatment interruption). Therefore, the profile of peripheral nerve disorders in Japanese patients as an adverse event of particular interest will be determined (i.e., information useful for continuation of treatment with Adcetris, including risk factors, commonly reported time to onset, outcomes, and the status of treatment with Adcetris, will be collected).

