1.3 Level of significance and confidence coefficient

Level of significance: Two-sided 5%

Confidence coefficient: Two-sided 95%

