4.0 Treatment Given

4.1 Treatment given

(1) Analysis sets to be used

Safety analysis set, safety analysis set (Hodgkin’s lymphoma), and safety analysis set (anaplastic large-cell lymphoma)

(2) Data to be analyzed

For each data item, patients will be stratified into the following categories below, and the frequency will be calculated. In addition, summary statistics of continuous variable will be calculated:

Data item	Category
Initial dose of Adcetris	<1.2 mg/kg, 1.2 mg/kg, >1.2 mg/kg to <1.8 mg/kg, 1.8 mg/kg, or >1.8 mg/kg
Mean dose of Adcetris	<1.2 mg/kg, 1.2 mg/kg, >1.2 mg/kg to <1.8 mg/kg, 1.8 mg/kg, or >1.8 mg/kg
Dose of Adcetris per 3 weeks	<1.2 mg/kg, 1.2 mg/kg, >1.2 mg/kg to <1.8 mg/kg, 1.8 mg/kg, or >1.8 mg/kg
Duration of treatment with Adcetris	1, 2, 3, 4, 5, 6, 7, 8, 9, 10, 11, 12, 13, 14, 15, 16, or ≥ 17 cycles
Reason(s) for discontinuation of Adcetris	Treatment goal achieved, adverse event(s), lost to follow-up, transfer to another hospital, pregnancy, inadequate response, and/or other
Post-baseline hematopoietic stem cell transplantation	Absent, present, or unknown
Type of post-baseline hematopoietic stem cell transplantation	Autologous or homologous
Days from the date of the last dose of Adcetris to hematopoietic stem cell transplantation (autologous) (Post-baseline hematopoietic stem cell transplantation: autologous)	-
Duration of treatment with Adcetris prior to	-

hematopoietic stem cell transplantation (autologous) (Post-baseline hematopoietic stem cell transplantation: autologous)	
Days from the date of the last dose of Adcetris to hematopoietic stem cell transplantation (homologous) (Post-baseline hematopoietic stem cell transplantation: homologous)	-
Duration of treatment with Adcetris prior to hematopoietic stem cell transplantation (homologous) (Post-baseline hematopoietic stem cell transplantation: homologous)	-
Drug(s) other than Adcetris used for the treatment of the primary disease	Absent or present
Drug(s) used for the prevention of infection	Absent or present
Specific drug(s) used for the prevention of infection	Antibiotics/synthetic antibacterial agents, antifungals, antivirals, trimethoprim-sulfamethoxazole combinations, and/or other prophylactics against infections

(3) Figure/table number

Tables 4.1-1 to 4.1-3

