5.2.4 Occurrence of adverse drug reactions/infections by CTCAE Grade (the worst one)

(1) Analysis sets to be used

Safety analysis set, safety analysis set (Hodgkin’s lymphoma), and safety analysis set (anaplastic large-cell lymphoma)

(2) Data to be analyzed

For each data item, patients will be stratified into the following categories, and the type of adverse drug reactions, etc., will be analyzed:

Data item	Category
CTCAE Grade (the worst one)	≤Grade 2, ≥Grade 3, or unknown

The type of adverse drug reactions, etc., will be analyzed as follows:

Data item	Data to be analyzed
Type of adverse drug reactions, etc.	The incidence of adverse drug reactions, etc., for each CTCAE grade (the worst one) will be calculated by SOC and PT. For SOC, the number and percentage of patients with drug reactions, etc., will be calculated. For PT, the number and percentage of drug reactions, etc., will be calculated. SOCs will be presented in the internationally agreed order, and PTs will be presented in ascending order of HLGT and PT codes if their SOCs are “Investigations,” and in ascending order of PT code otherwise. The CTCAE grade (the worst one) is higher in the order of ≥Grade 3, ≤Grade 2, and unknown. If the same patient has multiple occurrences of the same adverse drug reaction, etc. (PT), the reaction with the highest CTCAE grade will be counted once per patient.

(3) Figure/table number

Tables 5.2.4-1 to 5.2.4-3

5.3 Percentage of patients with adverse drug reactions/infections by patient demographics and baseline characteristics and treatment given

(1) Analysis sets to be used

Safety analysis set, safety analysis set (Hodgkin’s lymphoma), and safety analysis set (anaplastic large-cell lymphoma)

(2) Data to be analyzed

For each data item, patients will be stratified into the following categories, and the percentage of patients with adverse drug reactions, etc. (with point estimate and 95% confidence interval) will be determined.

For categories associated and not associated with ranking, Fisher’s exact and Mann-Whitney U tests, respectively, will be used. If there is a category of “unknown,” it will be excluded to perform

the Mann-Whitney U test.

Data item	Category
Sex	Male or female
Age	<18 years, 18 to 64 years, 65 to 74 years, or ≥ 75 years
Disease duration	<1 year, <1 to 3 years, <3 to 5 years, ≥ 5 years, or unknown
ALK (for patients with anaplastic large-cell lymphoma)	Positive, negative, or unknown
Clinical stage	I, II, III, IV, or unknown

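### Cycles received enter none of the risk-factor tables (SAP 5.3, 5.9.2, 5.9.7), so a factor linked to stopping early for reasons other than the event is biased toward looking protective.

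*SAP*

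**What the plan says.** SAP 5.9.2 describes its table of drug-related neuropathy thus: "patients will be stratified into the categories below, and the incidence of peripheral nerve disorders considered related to Adcetris will be calculated by CTCAE Grade". Strata include sex, age, disease duration, ECOG status, weight, prior therapy and three dose measures. SAP 5.9.7 has the same form for neutropenia, by prior transplant, baseline neutrophil grade and infection prophylaxis; Supplemental SAP 2, 2.1.1 repeats that table. In SAP 5.3 the outcome is any adverse drug reaction: "the percentage of patients with adverse drug reactions, etc. (with point estimate and 95% confidence interval) will be determined", with a Fisher or Mann-Whitney test per factor. Sections 5.9.2 and 5.9.7 name no test.

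The SAP's definition of the percentage of patients with events divides by the number of patients and has no exposure term. SAP 4.1 tabulates "Duration of treatment with Adcetris" in the categories "1, 2, 3, 4, 5, 6, 7, 8, 9, 10, 11, 12, 13, 14, 15, 16, or ≥ 17 cycles", and that item does not reappear in 5.3, 5.9.2 or 5.9.7. The treatment items there are initial dose, mean dose and dose per 3 weeks.

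Protocol 9.2.5 collects adverse events until 16 cycles are complete or treatment is discontinued. On neuropathy it says that information will be collected "including risk factors, commonly reported time to onset, outcomes, and the status of treatment with Adcetris". Protocol 10.4.2 asks for event frequency by background factor and by treatment given.

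**The concern.** A patient observed for one cycle counts the same in these tables as one observed for sixteen. Because collection stops with treatment, a stratum whose patients stop sooner has less time in which an event can be seen. If they stop for reasons unrelated to the event, the crude percentage falls even when the risk per cycle is the same.

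SAP 4.1 lists such reasons: treatment goal achieved, inadequate response, transfer to another hospital. It is plausible that some of them vary with age, performance status or prior transplant, though the documents do not say so. The tables meant to show which patients are prone to neuropathy or neutropenia could then credit a factor with protection it does not give, or hide a real one.

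The dose items do not repair this. Mean dose is divided by the number of cycles and dose per 3 weeks by elapsed time, so both measure level or intensity and not length of observation. The onset tables (5.2.1, 5.2.3) count events per time window without a number at risk, and the listings in 5.10 and 5.11 cover only patients who had the event.

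**Working it through.** **The plan's own figure.** Protocol 3.2 gives event frequencies that "were 56%, 61%, 20%, 11%, and 6%, respectively" for neuropathy, infections, neutropenia of Grade 3 or higher, infusion reaction and pulmonary disorder. It says that seeing at least 10 infusion reactions "with a probability of 95% would require 140 patients". Exact binomial: P(X ≥ 10 | n = 140, p = 0.11) = 0.952, and n = 139 gives 0.949, so 140 is the smallest such n. For pulmonary disorder, P(X ≥ 4 | n = 140, p = 0.06) = 0.971. The figure reproduces. It is a target for seeing events; the documents give no power or effect size for comparing strata.

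**Size of the bias when the factor has no effect.** From the documents: 56% neuropathy. Assumed: constant hazard h per cycle, 56% reached at 9 cycles, and every patient in a stratum treated for the same number of cycles c.

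- h = −ln(1 − 0.56)/9 = 0.821/9 = 0.0912 per cycle
- Crude percentage after c cycles = 1 − exp(−ch)
- Mean cycles at risk per patient, up to the first event = (1 − exp(−ch))/h

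| Cycles received | Crude % with event | Mean cycles at risk | First events per 100 cycles at risk |
|---|---|---|---|
| 4 | 30.6 | 3.35 | 9.1 |
| 6 | 42.2 | 4.62 | 9.1 |
| 8 | 51.8 | 5.68 | 9.1 |
| 10 | 59.8 | 6.56 | 9.1 |

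The crude percentages differ by up to 29 points and the rate per cycle at risk does not differ. The choice of 9 cycles matters: if 56% is reached at 6 cycles, 4 against 10 cycles shows 42% against 75%; if at 12 cycles, 24% against 50%.

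**Direction of the bias.** Assumed: h = 1 − 0.44^(1/16) = 0.050 per cycle, a 16-cycle limit, and a probability s per cycle of stopping for unrelated reasons. With a = (1 − h)(1 − s), the crude percentage is h(1 − a^16)/(1 − a).

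| Stratum | h | s | Crude % |
|---|---|---|---|
| Reference | 0.05 | 0.05 | 41 |
| No true effect, more unrelated stopping | 0.05 | 0.20 | 21 |
| Doubled hazard, same unrelated stopping | 0.10 | 0.05 | 63 |
| Doubled hazard, somewhat more unrelated stopping | 0.10 | 0.10 | 51 |
| Doubled hazard, much more unrelated stopping | 0.10 | 0.20 | 36 |

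The second row is a null factor that looks protective. The last is a true risk factor that looks protective (36% against 41%). In the third row treatment is also shorter than in the reference: a mean of 8.8 cycles if half of the affected patients stop because of the event and 6.3 if all do, against 9.7 (reference, half stopping). The factor still looks harmful.

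**The case against.** A reader might infer that cycles received enter no safety analysis at all. They do enter one: SAP 5.9.12 uses the number of doses given as the denominator for infusion reactions. The gap is confined here to the risk-factor tables.

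A reader might also infer that any factor linked to early stopping will look protective. The documents do not support that. Adverse events are a listed reason for discontinuation, and where the event itself ends treatment a harmful factor still looks harmful (third row of the second table). The bias runs toward protection only for stopping unrelated to the event.

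A third tempting reading is that the plan's tests will report false factors at a known rate. With 30 against 110 patients and the assumptions of the first table, a two-sided 5% Fisher test would reject in 80% of cases for 4 against 10 cycles, 36% for 6 against 10 and 10% for 8 against 10. With 15 against 125 patients, 4 against 10 cycles gives 52%. But 5.9.2 and 5.9.7 name no test, the tests in 5.3 concern any adverse drug reaction, for which the documents give no frequency, and the group sizes are invented. These rates are hypothetical.

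The best defence is that Protocol 10.4.2 asks for exactly this frequency, and that the proportion affected during treatment as actually given is a legitimate description of routine use. That stands, and it is why the crude percentages should stay. It does not make them a measure of risk per unit of treatment, which a statement about risk factors needs.

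Protocol 7.4 follows patients who stop because of an adverse event, but only until that event resolves or improves; it does not extend the search for new events.

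**Conclusion.** The point holds for SAP 5.3, 5.9.2 and 5.9.7. They compare crude patient percentages across strata, length of treatment varies widely, observation ends with treatment, and nothing in the tables accounts for it. A factor linked to stopping early for reasons other than the event is biased toward looking protective, and a true risk factor can be masked.

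The size cannot be read from the documents, which give no distribution of cycles, no shape of the hazard and no link between any baseline factor and stopping. Under the assumptions above, the difference with no true effect runs from 8 points (8 against 10 cycles) to 29 points (4 against 10). Events concentrated in the early cycles would shrink it. The 140-patient target is unaffected. This is a worthwhile, inexpensive improvement to the analysis; it does not invalidate the descriptive tables.

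**What to change.** Keep the crude percentages. In 5.9.2, 5.9.7 (with its repeat in Supplemental SAP 2, 2.1.1) and 5.3, add beside them for each stratum:

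- the number of cycles at risk, counted to the first event, discontinuation or the end of Cycle 16;
- patients with a first event per 100 cycles at risk, with 95% confidence interval;
- cumulative incidence to the end of Cycles 4, 8 and 16 from time to first event, with 95% confidence interval.

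Where strata are large enough, after collapsing sparse levels, add a hazard ratio with 95% confidence interval as a supportive comparison. State that no risk or protective factor will be named from the crude percentage alone when the exposure-adjusted result disagrees. The hazard ratios should not become the sole basis for conclusions, because stopping may be informative and many strata will be small.

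The cost is SAP wording and some programming; onset dates and dosing dates per cycle are already collected. The downsides should be stated with the results: more columns, loss of events with unknown onset dates from the timed analysis, possibly informative stopping (adverse event and inadequate response are listed reasons), and imprecise estimates in small strata, above all within the separate Hodgkin's and anaplastic large-cell sets.
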